1.0 Objectives

1.1 Purpose, specific aims, and/or objectives.

This proposed study aims to develop group-based trajectory models to identify patients with similar medication filling behavior among patients with co-morbid hypertension (HTN) and diabetes (DM) using angiotensin converting enzyme inhibitors (ACE) or angiotensin receptor blockers (ARB). A motivational interviewing (MI) pharmacy student telephone intervention will then be customized by the identified trajectories and tested to demonstrate effectiveness in improving ACE/ARB adherence.

1.2 Hypothesis

It is our central hypothesis that the customized MI based pharmacy student intervention will be beneficial in improving medication adherence to ACEI/ARBs.

2.0 Background

2.1 Diabetes (DM) and hypertension (HTN) are independent risk factors for cardiovascular (CV) disease and major public health issues in the United States (US). The two conditions frequently coexist, with 70-80% of DM patients also having HTN. The combination significantly increases the risk of macrovascular and microvascular DM complications. Controlling high blood pressure (BP) can greatly reduce these complications including the CV risk which accounts for 50-80% of DM fatalities. Angiotensin converting enzyme inhibitors (ACE) and Angiotensin receptor blockers (ARB) are highly recommended for patients with DM and HTN, with a well-documented benefit in reducing DM complications.

The project will have 2 phases: Phase 1 will be a retrospective analysis of 12 month refill data to determine patient past adherence behavior patterns. Phase 2 will entail a prospective randomized design among non-adherent patients to evaluate the effectiveness of the customized intervention. The students will contact patients assigned to the intervention group and follow a protocol using the Ask-Provide-Ask approach of MI given the patient adherence pattern for a tailored education. Monthly follow-up calls for 6 months will be carried out. Adherence during the 6 and 12 months post-intervention, will be evaluated for the intervention and control groups.

Findings are expected to demonstrate the effectiveness of an innovative low cost intervention in improving adherence and have a positive impact in implementing tailored interventions leading to more desirable long term health outcomes and considerable cost savings in our financially overwhelmed healthcare system.

2.2 The primary investigator has conducted prior research collaborating with Cigna Healthspring using motivational interviewing techniques over phone calls. The IRB reference of the last study is: 16410-01-(7926)

3.0 Inclusion and Exclusion Criteria

- 3.1 Inclusion Criteria: Patients over the age of 18, with continuous enrollment in the Cigna Medicare Advantage health plan in Texas starting July, 2016 until January 2018 with a diagnosis of comorbid DM and HTN and having a prescription filled for an ACEI or ARB medication during the month of January, 2017. The patient identification period will be included in the study. Patients who disenroll or die before the study ends will be excluded from the study.. Exclusion criteria include having a diagnosis (identified by ICD-10 codes) for dementia, or an ACEI/ARBS contraindication like angioedema, hyperkalemia, renal artery stenosis.
- 3.2 Describe how potential subjects will be screened for eligibility based on these criteria: The retrospective analysis will apply these exclusion and inclusion criteria during the data analysis stage to give the final cohort of patients.
- 3.3 This study will not include any vulnerable population, mentioned below:
 1. Adults unable to consent
 2. Individuals who are not yet adults (infants, children, teenagers)
 3. Pregnant women
 4. Prisoners
 5. Students for whom you have direct access to/influence on grades
 6. Economically and/or educationally disadvantaged persons

4.0 Vulnerable Populations

4.1 N/A

5.0 Number of Subjects

- 5.1 This study will have two phases. In the retrospective analysis stage, Cigna Healthspring will provide data on patients who fulfill eligibility criteria mentioned above. It is expected that this data will have approximately 22,000 patients with DM and HTN.
- 5.2 In the intervention phase, 250-300 patients will be included in the intervention phase. If 1 control is used for each patient in the intervention group, the total sample of phase 2 is expected to be 500-600.

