6.0 Recruitment Methods

LOCAL:

- 6.1 This study will start with the retrospective phase which does not involve recruitment of patients, but involves analysis of existing data. De-identified data will be obtained from Cigna-Healthspring.
- 6.2 The project will be implemented in collaboration with Cigna-Health Spring, a Medicare Advantage Plan in Texas. The health plan has several electronic data files available for analysis including membership file, member

A motivational interviewing intervention customized by patient adherence patterns (NCT03985098) – 03.28.2018

summary file, institutional claims file, professional claims file, quest lab, Cigna-Health Spring's medical claims file (CCMS) and pharmacy file. Pharmacy files contain Part D pharmacy data provided by pharmacy benefits manager including patient/ drug identifying information, fill dates, days of supply, quantity dispensed and dosing for each prescription filled. The refill data will be used to determine the non-adherent patients. ICD-10 codes will be used to determine other exclusions using professional claims data.

Phase 2 will involve project intervention which will be conducted over the phone. A list of actively enrolled members, taking the medication who were a part of phase 1 will be created by Cigna HealthSpring to be used for intervention implementation at their premises. The phone call will be made by University of Houston pharmacy students who will be on rotation at Cigna-HealthSpring. The form of informed consent which will be read to the patient is attached to the IRB. If the patient consents to receive the intervention over the phone, and completes the phone call, the patient forms a part of the intervention group. Five follow-up phones will be attempted one month apart for the patient after the initial call.

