9.3 Phase 2: intervention implementation

Patients that are still enrolled in the health plan during 2017-2018 will be included in phase 2. Patients will be categorized by their adherence trajectory identified in phase 1 and will be randomized to intervention vs. not within each category. The proposed intervention will be a telephone call by a pharmacy student participating in rotations at Cigna-Health Spring Plan and trained in MI and 6 monthly follow up calls. During implementation, students will first examine the patient adherence pattern that was identified in phase 1 which will be coded. The student will then confirm the diagnosis, medication name, and dose with the patient answering the call and will follow the outlined protocol. Using MI, students will assess readiness for change, help patients identify potential barriers in accordance with patient past pattern of use, and guide them to develop a plan to deal with these barriers

A motivational interviewing intervention customized by patient adherence patterns (NCT03985098) – 03.28.2018

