Additionally, the students will ask the 2 questions from the Patient Health Questionnaire (PHQ)-2, a validated screening tool for depression (attached). If the patient responds positively to either question, the student will suggest that the patient schedules an appointment with his/her healthcare provider to discuss these symptoms. The Supervising pharmacists will be available to assist the students in answering any medication related questions that may arise during the calls and arrange for a diabetes educator to contact the patient at a later time if needed. Follow up phone calls will be performed each month for a total of six calls. Students will be supervised by the pharmacist preceptors and managed care pharmacy residents throughout the calls and intervention implementation. The students who will be implementing the calls will attend a three day MI training facilitated by [name], who is experienced in utilizing motivational interviewing to improve adherence. The students will practice calls as a part of their training. They will also complete Human Subjects Research training before their rotation at Cigna Healthspring, and the certificates will be uploaded to the IRB application. After each initial call, students will record the date and write a summary of the interaction with the patient documenting the main barrier/s identified in the conversation and the plan made with the patient. During the follow up calls, students will emphasize the information, confirm problem solved, provide further encouragement and reinforce adherence.

Control group: For every patient that received a call, a control will be randomly selected from the list of patients randomly assigned to the control group.

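### Section 9.3 analyses one control per called patient and leaves out any other randomised controls, although the health plan already holds their refill records

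*Combined protocol and SAP*

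**What the plan says.** Section 5.2 sets the size of the called group, "In the intervention phase, 250-300 patients will be included in the intervention phase", and then gives the Phase 2 total conditionally: "If 1 control is used for each patient in the intervention group, the total sample of phase 2 is expected to be 500-600". Section 9.3 is firmer. Patients are grouped by their Phase 1 trajectory and "will be randomized to intervention vs. not within each category". Under its control-group paragraph, "For every patient that received a call, a control will be randomly selected from the list of patients randomly assigned to the control group". It does not say whether that draw is made within trajectory category.

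The outcome in both groups is PDC at 6 and 12 months, calculated from refill data (section 20.1, outcome analysis). Section 6.2 describes the source: "Pharmacy files contain Part D pharmacy data provided by pharmacy benefits manager". No call to controls, or other contact with them, is described.

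The protocol does not give the randomisation ratio, the number randomised, the length of the control list, a reason for stopping at one control, or a power calculation.

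**The concern.** The students' capacity to make calls limits the intervention group. It does not limit the control group, whose outcome is read from existing records. Drawing a sample from the control list makes sense only if the list is longer than the sample, so section 9.3 implies that some patients are randomised to control and then not analysed. Their omission widens the confidence interval for the difference in PDC. Because no power calculation shows that 500-600 patients are enough, precision that is available without further enrolment should not be given up without a stated reason.

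**Working it through.** **Inputs from the protocol.** Called patients n = 250 to 300 (5.2); one control per called patient (9.3; conditional in 5.2); Phase 2 total 500 to 600 (5.2); comparison of mean PDC by t-test (20.1).

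**Assumptions, none of them in the protocol.** Two-sided 5% test, 80% power (multiplier 1.96 + 0.84 = 2.80), and a PDC standard deviation of 0.20 to 0.30, equal in both groups.

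**1. The stated total.** 250 × 2 = 500 and 300 × 2 = 600. The figure in 5.2 is reproduced.

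**2. Standard error with more controls.** With n called patients and k controls for each, SE = SD × √(1/n + 1/(kn)). Relative to one-to-one this is √((1 + 1/k)/2), whatever n and SD are. The last column gives the power for an effect that has 80% power at one-to-one.

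| Controls per called patient (k) | Relative SE | Fall in SE | Power |
|---|---|---|---|
| 1 | 1.000 | none | 80% |
| 1.33 | 0.935 | 6.5% | 85% |
| 2 | 0.866 | 13% | 90% |
| 4 | 0.791 | 21% | 94% |
| no limit | 0.707 | 29% | 98% |

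**3. Which row applies.** This cannot be determined from the protocol. As an illustration, if randomisation were 1:1 and a share c of those assigned to intervention were called, the list would hold 1/c controls per called patient: 1.33 at c = 75%, 2 at c = 50%, 4 at c = 25%.

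**4. Detectable difference in mean PDC.** This is 2.80 × SD × √((1 + 1/k)/n).

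- One-to-one: from 2.80 × 0.20 × √(2/300) = 0.046 to 2.80 × 0.30 × √(2/250) = 0.075.
- Four-to-one: from 2.80 × 0.20 × √(1.25/300) = 0.036 to 2.80 × 0.30 × √(1.25/250) = 0.059.

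**5. The intent-to-treat comparison.** Steps 2 to 4 hold the intervention group at the called patients. Section 6.2 counts a patient in that group only after consent and a completed first call. Intent to treat needs everyone randomised to be called. Assume 1:1 randomisation and no effect in uncalled patients, and take an effect with 80% power in the one-to-one called comparison. Each arm then has n/c patients and the mean effect shrinks by the factor c, so the standardised effect is 2.80 × √c.

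- c = 75%: 2.80 × 0.866 = 2.43, power 68%.
- c = 50%: 2.80 × 0.707 = 1.98, power 51%.
- c = 25%: 2.80 × 0.5 = 1.40, power 29%.

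With an unlimited control list the standardised effect is 2.80 × √(2c), and power is about 93%, 80% and 51%. The gains in steps 2 and 4 therefore do not describe this analysis.

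**The case against.** The strongest reply is that the gain is unknown and may be small. A reader might infer a very long control list from section 5.1: "It is expected that this data will have approximately 22,000 patients with DM and HTN". The protocol does not support that. The figure is the Phase 1 cohort, whereas Phase 2 takes only the non-adherent (2.1) who are still enrolled and taking the medication (6.2), and their number is not given. Section 5.2 also leaves the ratio open. This part of the reply stands, and it is why the gain is given as a range.

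A reader might also infer that the extra controls are free. The protocol shows only that the records exist and that no contact with controls is described. The health plan must still de-identify and share the data (10.2), and the cost of doing so is not stated.

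Finally, a reader might take the one-to-one draw as the breach of intent to treat, or as a source of bias. A random draw from randomised controls loses precision but leaves the expected control mean unchanged. The conflict with intent to treat comes chiefly from section 6.2, which defines the intervention group by consent and completion. Adding controls does not remove that selection.

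The need for a start date for each control is no reason to keep the draw. Follow-up runs from the initial call, which controls do not have, so the one-to-one design needs such a date too.

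**Conclusion.** The point holds as one of precision. Section 9.3 leaves out any randomised controls beyond one per called patient, and no reason is given. For the called-versus-control comparison, using the full list would lower the standard error by 6.5% to 21% for lists of 1.33 to 4 controls per called patient, with a ceiling of 29%. Under the assumed two-sided 5% test, 80% power and SD of 0.20 to 0.30, the detectable PDC difference with 250-300 called falls from about 0.046-0.075 at one-to-one to 0.036-0.059 at four-to-one.

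Two limits apply. The actual gain depends on a list size that the protocol does not state. The figures also do not apply to the promised intent-to-treat analysis, whose power depends mainly on how many of those randomised to be called complete the call. Nothing in the protocol shows that 500-600 is inadequate, since it states no target difference or power.

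**What to change.** In 5.2 and 9.3:

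- State the randomisation ratio and the expected length of the control list.
- Replace the one-to-one draw with all patients randomised to control in each trajectory category, and restate the Phase 2 total.
- Adjust the analysis in 20.1 for trajectory category. If call completion differs between categories, the ratio of controls to called patients will differ too, and a plain t-test would mix that imbalance with the effect.
- Give each control an assigned follow-up start date, spread over the same calendar period as the calls (enrolment runs 8 months under 7.4).
- For the intent-to-treat analysis, keep everyone randomised to be called, not only those who meet the definition in 6.2, and size that comparison for the expected uptake. The called-versus-control comparison can be reported beside it, labelled as such.

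If the one-to-one sample is kept, give the reason. The change needs no further calls or enrolment. Its cost is a larger de-identified extract from the health plan and start dates for more controls.

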6.0 Recruitment Methods

LOCAL:

- 6.1 This study will start with the retrospective phase which does not involve recruitment of patients, but involves analysis of existing data. De-identified data will be obtained from Cigna-Healthspring.
- 6.2 The project will be implemented in collaboration with Cigna-Health Spring, a Medicare Advantage Plan in Texas. The health plan has several electronic data files available for analysis including membership file, member

A motivational interviewing intervention customized by patient adherence patterns (NCT03985098) – 03.28.2018

summary file, institutional claims file, professional claims file, quest lab, Cigna-Health Spring's medical claims file (CCMS) and pharmacy file. Pharmacy files contain Part D pharmacy data provided by pharmacy benefits manager including patient/ drug identifying information, fill dates, days of supply, quantity dispensed and dosing for each prescription filled. The refill data will be used to determine the non-adherent patients. ICD-10 codes will be used to determine other exclusions using professional claims data.

Phase 2 will involve project intervention which will be conducted over the phone. A list of actively enrolled members, taking the medication who were a part of phase 1 will be created by Cigna HealthSpring to be used for intervention implementation at their premises. The phone call will be made by University of Houston pharmacy students who will be on rotation at Cigna-HealthSpring. The form of informed consent which will be read to the patient is attached to the IRB. If the patient consents to receive the intervention over the phone, and completes the phone call, the patient forms a part of the intervention group. Five follow-up phones will be attempted one month apart for the patient after the initial call.

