Customization of intervention: After completion of the retrospective analysis phase and identifying the major trajectories in this patient population, the team will meet to discuss the patterns identified, the potential barriers likely to be associated with each trajectory, and strategies that can help patients within each trajectory based on their behavior pattern. The team will then develop customized education specific to each identified trajectory. For example: some patients can have high medication use in the early part of the follow up period but poor after, others may have low initial use and improved subsequent. Some may have intermittent adherence throughout the follow up time, others may simply discontinue. The expected barrier and potential solutions that should be discussed with the patient using MI strategies will vary accordingly. Patients past adherence patterns will guide the team in determining probable barriers and what can potentially help the patient. For example, patients who discontinue the medication may have side effects concerns or may view the medication as unnecessary. Patients who continue to take medication but have less than 0.8 PDC throughout may be forgetting to take the medicine and need help remembering. The team will create a code for each trajectory identified to categorize the patients. A protocol for each trajectory will be developed to summarize the education that is likely to benefit patients with the specific behavior pattern given the code. All the developed protocols will be based on the Ask-Provide-Ask approach, a pharmacist adaptation for the Elicit-Provide-Elicit approach of MI (attached)

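### Section 6.2 limits the call list to members taking the medication, while section 9.3 puts no such condition on randomisation or on the control draw

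*Combined protocol and SAP*

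**What the plan says.** Several places bear on who enters Phase 2.

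- **Section 6.2:** "A list of actively enrolled members, taking the medication who were a part of phase 1 will be created by Cigna HealthSpring". The list is "to be used for intervention implementation at their premises". No date, fill window or data source is given for being on the drug.
- **Section 9.3, opening:** "Patients that are still enrolled in the health plan during 2017-2018 will be included in phase 2". These patients are grouped by Phase 1 trajectory and "will be randomized to intervention vs. not within each category".
- **Section 9.3, control group paragraph:** one control per called patient is drawn at random from those assigned to control. Neither current use nor matching on trajectory is mentioned.
- **Section 9, customisation of the intervention (between 9.2 and 9.3):** stopping the drug is one of the example patterns, and its likely barriers are discussed: "patients who discontinue the medication may have side effects concerns".
- **Section 2.1:** Phase 2 is a "prospective randomized design among non-adherent patients".
- **Section 3.1:** Phase 1 requires "continuous enrollment in the Cigna Medicare Advantage health plan in Texas starting July, 2016 until January 2018", and adds: "Patients who disenroll or die before the study ends will be excluded from the study".
- **Section 20.1:** the analysis is by intent to treat. Baseline PDC over the 12 months before the intervention and past trajectory are compared between arms, with regression adjustment if a difference is significant.

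**The concern.** The plan describes two different Phase 2 populations. Section 6.2 would leave out patients who are no longer on the drug. Section 9.3 would randomise them, and the customisation text prepares education for them.

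PDC is the outcome, and a patient who has stopped and does not restart has a follow-up PDC near zero. If such patients are filtered from the called arm but stay in the pool from which controls are drawn, the arms differ before any call is made, and the difference favours the intervention. If they are filtered from both arms, the comparison is fair, but one of the patterns the tailoring was built for is never tested.

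**Working it through.** **The plan's own figure.** Section 5.2 gives 250–300 intervention patients and one control each: 2 × 250 = 500 and 2 × 300 = 600, as stated. The documents give no alpha, power, SD, target difference or share of discontinuers, so everything numerical below rests on assumptions.

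**The texts side by side.**

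| Condition | Call list (6.2) | Randomisation (9.3) | Control draw (9.3) |
|---|---|---|---|
| Enrolment | yes | yes | inherited from randomisation |
| Current use | yes, undefined | not stated | not stated |
| Discontinuers | out, read literally | in, as a trajectory category | in |

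**Effect of the order.**

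- List first, then randomisation: both arms lose discontinuers, and bias by this route is 0.
- Randomisation first, then list: only the called arm loses them.

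**Bias under the second order.** Let f be the share of discontinuers among randomised patients and g the gap in mean follow-up PDC between the other patients and the discontinuers. With no true effect, the called-arm mean is m and the control mean is (1 − f)m + f(m − g) = m − fg. The spurious difference is therefore f × g. This assumes that all discontinuers leave the called arm and none leave the control arm.

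- Low end: 0.05 × 0.2 = 0.01
- 0.10 × 0.4 = 0.04
- 0.20 × 0.4 = 0.08
- High end: 0.30 × 0.5 = 0.15

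**Scale.** Assume SD 0.30 and two-sided alpha 0.05. The standard error is 0.30 × √(2/n), which is 0.0268 at n = 250 per arm and 0.0245 at n = 300. The difference detectable with 80% power is (1.960 + 0.842) × SE, or 0.075 and 0.069.

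The false-positive rate of the unadjusted t-test is Φ(fg/SE − 1.96) + Φ(−fg/SE − 1.96):

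| f | g | Bias in PDC | n = 250 | n = 300 |
|---|---|---|---|---|
| 5% | 0.2 | 0.01 | 7% | 7% |
| 10% | 0.4 | 0.04 | 32% | 37% |
| 20% | 0.4 | 0.08 | 85% | 90% |

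**Would the planned baseline check catch it?** Suppose the missing patients are those with a Phase 1 discontinuer trajectory.

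- 0/250 against 25/250: chi-square = 500 × (250 × 25)² / (250 × 250 × 25 × 475) = 26.3, p < 0.0001.
- 0/250 against 12/250: chi-square = 500 × (250 × 12)² / (250 × 250 × 12 × 488) = 12.3, p about 0.0005.

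Either result would trigger the planned regression. With trajectory as a categorical term, a category containing only controls adds nothing to the group contrast, so most or all of this bias would go. The estimate would then say nothing about discontinuers.

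The check is weaker for patients who stopped after the Phase 1 data ended in January 2018. They carry another trajectory label, and a recent stop may lower the 12-month baseline PDC only a little. Use of the drug at the time of the call is not among the characteristics compared.

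**The case against.** The best defence is that the list is the common Phase 2 frame, made before randomisation, and that being on the medication loosely describes the ACEI/ARB cohort. Sections 8.1 and 9.1 use similarly broad terms for a cohort that includes later discontinuers. Randomising within each trajectory also suggests that discontinuers are meant to be in. On that reading there is no bias and perhaps no exclusion.

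This reading is open, but the text does not establish it. Every Phase 1 patient filled one of the drugs in January 2017, so the phrase adds nothing to Phase 1 membership unless it means something more current. The list's stated purpose is the intervention, and section 16.1 has callers working from a list of people to contact, which would not include controls. Neither point proves the order.

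Intent to treat in section 20.1 would help if everyone randomised were analysed. But 6.2 counts as intervention patients those who consent and complete the call, and 9.3 draws one control per called patient. That conflict is a separate matter; here it means that the stated principle does not by itself keep uncalled discontinuers in the analysis.

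The baseline comparison is a real safeguard, as shown in the working, and it limits how much weight the unadjusted figures can bear.

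A reader might also infer three stronger things that the documents do not support:

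- **That controls have no enrolment filter.** Section 9.3 applies enrolment before randomisation, so to both arms, and the exclusion in 3.1 for disenrolment or death is not limited to one arm.
- **That the 9.3 filter is empty because every Phase 1 patient already meets it.** This holds only if enrolment to January 2018 is enough; read as enrolment through 2018, the filter does exclude people.
- **That the enrolment window closes before calls begin.** Section 7 numbers study months without a calendar start, so this cannot be shown.

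**Conclusion.** The conflict between 6.2, the customisation text and 9.3 is real, and the plan should resolve it before randomisation. It is not a demonstrated bias. One-sided loss of discontinuers needs two things the documents leave open: that the condition means current use, and that it is applied after randomisation. If both hold, the bias favours the intervention. If the condition is applied first, the cost is a narrower target population.

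The size is a conditional illustration: about 0.01–0.15 PDC before adjustment, for assumed discontinuer shares of 5–30% and gaps of 0.2–0.5. It runs from negligible to about twice the 0.069–0.075 detectable at an assumed SD of 0.30. The planned baseline check would probably detect and reduce a large imbalance by Phase 1 trajectory, but less surely one from patients who stopped later.

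**What to change.** Reconcile 6.2, the customisation paragraph and 9.3 into one Phase 2 eligibility rule that:

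- says whether current use is required, and so whether discontinuers are in or out;
- if it is required, defines it from the pharmacy file with a stated date or fill window;
- requires enrolment on the randomisation date, in place of the 2017–2018 period;
- is applied once, to all Phase 1 candidates, before randomisation, so that the call list and the control list come from the same set.

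The section 6.2 list then becomes the intervention-arm part of that set, with no further filter. If discontinuers are out, the customisation text should say that education for that pattern will not be tested.

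The cost is wording in 6.2, 9.3 and possibly the customisation paragraph, plus one eligibility run at the health plan. Provided enough eligible patients remain, the 500–600 total does not change, and bias by this route is 0.
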